5-All functional tests are aimed at obtaining an understanding of the impact of fibromyalgia disease on their quality of life.

Familiarization

Familiarization will consist of 2 phases:

1- Familiarization with the functional tests to be performed (on the same day as the tests).

- 1- How they are performed and explanation of each test visually.
- 2- Consideration before performing the tests and resolving doubts.

2- Familiarization with the occlusive training and material:

- 1- The resting SBP will be taken to establish the training pressure of each participant.

(measurement carried out by a team of nurses from Santa Ángela de la Cruz Hospital. Viamed)

- The cuff pressure will be reflected by the SBP at rest in the arm measured with a tensiometer, to which 20% will be added to establish the SBP at rest of the lower body.
- 20% will be added to the resting SBP of the lower body to establish the lower body cuff pressure.

- At no time should the cuff pressure exceed 7 % on the visual pain scale (VAS).

2- Familiarization with the material will be completed when each volunteer is able to put on, establish the previously set pressure on a chair and walk with the material.

3- The volunteer should become familiar with the intensity of the exercise. Borg scale 1-10, will be used at all times to establish the relative intensity of each participant at all times, the intensity being no less than 6 and more than 7 points, so several exercises will be performed with and without material for that purpose.

9-week Intervention Period

20 minutes of work with blood flow restriction walking at a relative intensity of 6-7 points on the modified Borg RPE scale in a 2 x 30 meter corridor, with each participant's round trip delimited. After 10 minutes, a non-active rest of 3 minutes of seated flow restriction will be performed, to be followed by another 10 minutes of walking.

Considerations for the intervention period and COVID-19:

- 1- The intervention period will be carried out 2 days per week (Tuesday and Friday) in the afternoon at the Viamed Santa Angela de la Cruz Hospital (Bellavista, Seville).
- 2- Each participant will have the necessary autonomy to carry out the training.
 - Placement of the material
 - Rest in a chair for 3-5 minutes without occlusion.
 - Before finishing the rest, re-set the pressure established for each participant.
- 3- Each participant will have to perform the training session with a surgical mask and the handling of the material will be with latex gloves that will be discarded after finishing the training session.
- 4- Each training session will be carried out with groups of 4 participants simultaneously.
- 5- Halfway through the intervention period, each participant's resting SBP will be measured again in order to make adjustments to the maguitar pressure.

Measurements for each session/participant (variables)

1- Before the beginning of each session:

- O2 saturation and resting heart rate.
 - Constants to check the safety of the beginning
- Motivation level (1-10) (additional information)
 - To be used as a subjective check of the patient in order to verify the weekly evolution and to anticipate solutions to possible complications of the volunteer (abandonment).
- Quality of sleep (very good, fairly good, fairly bad, very bad). Pittsburg Subjective Sleep Scale (additional information)
 - To be used as a subjective check of the patient with the aim of checking the weekly evolution and to anticipate solutions to possible complications of the volunteer (abandonment).
- Pain level (1-10) Visual Analog Pain Scale (VAS).

2- After each session:

- O2 saturation and heart rate
- Perceived intensity of exertion scale at the end of the modified Borg (1-10).
- Pain level (1-10) Visual Analog Pain Scale (VAS).

Timing of phases and weeks.

Phases:

- 1- Completion of questionnaire of criteria for inclusion in the research and items necessary to be part of it (to be carried out in the fibromyalgia association itself).
- 2- Blood sampling (to be carried out at the viamed hospital).
- 3- Previous evaluation of autonomy, quality of life and impact of the disease by means of questionnaires, tests and functional physical tests standardized for this purpose. It will be carried out at the Pablo de Olavide University facilities (CIRF).
- 4- Familiarization. It will be carried out at the Universidad Pablo de Olavide (CIRF) facilities.
- 5- Period of research intervention 9 weeks (18 supervised sessions). It will be carried out at viamed hospital. Pain Unit.
- 6- Final evaluation. It will be carried out in the facilities of Pablo de Olavide University (CIRF).

Weeks:

Week 1

- Monday: Pre-intervention blood sampling, disease impact questionnaires
- Wednesday: Familiarization 1 and functional tests nº 1,2 and 3
- Friday: Familiarization 2 and functional test nº 4

Week 2

- Monday: Familiarization 2 (material and training)
- Friday: Familiarization 2 (material and training)

Week 3 to week 12 (intervention period)

- Tuesday: Intervention period Intervention
- Friday: Intervention period

Week 13 Final evaluation.

- Monday: Post-intervention blood sampling, disease impact questionnaires
- Wednesday: Familiarization 1 and functional tests 1, 2 and 3.
- Friday: Functional test nº 4

Participants' arms.

Participants were divided into 2 non-randomized groups with a total of 37 participants at baseline and overcoming the different phases of exclusion 13.

- **Intervention group:** This group will perform each of the above research stages and perform the occlusive cuff intervention period. n= 7 participants.
- **Non-intervention group:** This group will perform each of the above research stages and will perform the intervention period without the occlusive cuff. n= 6 participants.

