Descriptive statistics were calculated for each variable. The normality of the distribution of data was verified by the Shapiro-Wilk test. Variables showing skewed distributions were log-transformed to obtain a normal distribution. Relative changes within each group were assessed using a paired Student's t test. To compare baseline variables the Student's t test, standardized differences ($\pm 90\%$ confidence level) and qualitative differences were estimated. To detect between-group differences, multiple 2 x 2 (group x time) mixed-analysis of variance was performed and adjustments for multiple comparisons were made using the Bonferroni method by dividing the significance level of 0.050 by the number of comparisons, additionally standardized differences ($\pm 90\%$ CL) and qualitative differences were estimated. The effect size of standardized differences was determined by Cohen's d statistic, and the Hopkins' scale was used to determine the magnitude of the effect size, where 0 to 0.19 = trivial, 0.20 to 0.59 = small, 0.60 to 1.19 = moderate, 1.2 to 1.99 = large, and >2 = very large (Hopkins et al 2009). A practically worthwhile difference was assumed when the difference score was ≥ 0.2 of the between-subject SD. Qualitative assessment indicates the likelihood for the between-group differences to be substantial, referring to possible differences, to likely, to very likely, and to almost certain differences. The probability of a true difference between groups was qualitatively classified as almost certainly not: $<0.5\%$; very unlikely: 0.5% to 5%; unlikely: 5% to 25%; possible: 25% to 75%; likely: 75% to 95%; very likely: 95% to 99.5%; and almost certain: $>99.5\%$. A substantial effect was defined as $>75\%$ (Batterham and Hopkins 2006).

Functional tests

30-second chair stand test

Objectives: (Test No. 1)

1-To assess the strength of the extensor muscles of the knees and hips, responsible for gait failure and falls in 30 seconds.

2-To evaluate the resistance to loss of lower body strength, which causes early fatigue, in 30 seconds.

3- To evaluate the perceived effort and relative intensity of the patient's effort.

Bibliographic references. Validity and standardization

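### A non-randomised 7 v 6 comparison is presented as an experimental test of the cuff, and its only formal between-group outcome test is an unadjusted change-score contrast

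*Combined protocol and SAP*

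**What the plan says.** The Methodology section describes an experimental design in which thigh-cuff pressure during walking is the independent variable, with outcomes measured before and after the intervention. Hypothesis 6 expects occlusive training to prove effective and safe.

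The Participants' arms section says: "Participants were divided into 2 non-randomized groups with a total of 37 participants at baseline and overcoming the different phases of exclusion 13". Seven people are in the cuff group. The six comparators "will perform the intervention period without the occlusive cuff". No allocation rule, matching or stratification is described.

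The Statistical analysis section sets out:

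- **Between-group test:** "To detect between-group differences, multiple 2 x 2 (group x time) mixed-analysis of variance was performed". No covariate is named.
- **Multiplicity:** "adjustments for multiple comparisons were made using the Bonferroni method by dividing the significance level of 0.050 by the number of comparisons". The number of comparisons is not given.
- **Baseline:** "To compare baseline variables the Student's t test, standardized differences" and qualitative differences are planned, but nothing is said about what follows if they show a gap.
- **A second route to a between-group claim:** "Qualitative assessment indicates the likelihood for the between-group differences to be substantial". The cut-off is a likelihood above 75%. A worthwhile difference is at least 0.2 of the between-subject SD.
- **Within-group change:** paired t tests in each group.

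No section limits causal interpretation.

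**The concern.** In a 2 x 2 layout with two time points, the group x time interaction is a two-sample t test on change. It removes any stable difference between the groups. Because the comparators also walk, it removes change that both groups share. It does not remove differential change related to baseline, such as unequal groups drifting back towards a common mean.

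Without randomisation there is no reason to expect the groups to start equal. The Study population section deliberately admits men and women aged 18 to 70, both active and sedentary. A difference in who entered which group could therefore appear as a cuff effect at or above the plan's own threshold.

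The >75% rule is the route most exposed to this in absolute terms. Bonferroni divides the significance level, and the likelihood rule does not use a significance level. With 13 non-randomised people, the language of an experimental test of an effective therapy claims more than the design can show.

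**Working it through.** **The plan's own figure.** The only sample-size calculation is for the precision of a prevalence: 1.96² x 0.018 x 0.982 / 0.03² = 75.4. This reproduces the stated 75 but does not size a two-group comparison.

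**Inputs from the plan.** 7 v 6 participants; two time points; significance level 0.05; worthwhile difference 0.2 SD; likelihood cut-off 75%. The Definition of variables section names nine questionnaires and physical tests before any blood measure: SS, WPI, FIQ, MFI-20, Time up and Go, chair stand, 6-minute walk, lower-body dynamometer and hand press.

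**Assumptions.** The plan gives neither a baseline gap D nor a pre-post correlation ρ. I take D = 0.5 or 1 SD (cuff group worse), ρ = 0.5/0.7/0.8, normal data with SD 1, two-sided tests, no true cuff effect, and nine comparisons for Bonferroni.

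**Step 1: equivalence.** In a test data set the interaction F and the squared t on change were both 0.1549.

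**Step 2: bias under regression to a common mean.** Size = (1 − ρ) x D.

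- D = 0.5: 0.5 x 0.5 = 0.25; 0.3 x 0.5 = 0.15; 0.2 x 0.5 = 0.10 SD.
- D = 1: 0.50, 0.30, 0.20 SD.

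So at 0.5 SD the bias passes 0.2 SD only when ρ = 0.5. At 1 SD it is at or above 0.2 SD throughout.

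**Step 3: error rates.** Simulation with 400,000 trials per cell. The interaction is a t test on change with 11 df. ANCOVA regresses the post value on group and baseline, with 10 df. The >75% rule is read as the probability of a benefit beyond 0.2 SD, with a flat prior. Entries are for ρ = 0.5/0.7/0.8.

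| Regressing gap | Rejects at 0.05 | Rejects at 0.05/9 (nominal 0.56%) | >75% rule declares benefit |
|---|---|---|---|
| None | 5% nominal | 0.56% nominal | 15/13/11% |
| 0.5 SD | 7.0/6.2/5.8% | 0.9/0.8/0.7% | 28/21/17% |
| 1 SD | 13.1/9.8/8.1% | 2.2/1.5/1.2% | 44/33/25% |

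At 0.05/15 (nominal 0.33%), a 1 SD gap gives 1.4/0.9/0.7%. On ANCOVA with the same 1 SD regressing gap, bias is 0, rejection at 0.05 is 4.9 to 5.0%, and the >75% rule fires in 15/14/12%.

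**Step 4: the opposite case.** If a 1 SD gap is stable, the change score is unbiased and rejects in 5.0%. ANCOVA then carries a bias of the same size in the other direction (0.50/0.30/0.20 SD) and rejects in 12.7/9.1/7.5% at 0.05. For a stable 0.5 SD gap the ANCOVA bias is 0.25/0.15/0.10 SD. Neither estimate is enough alone.

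**Step 5: what links the two estimates.** They differ by exactly (1 − fitted slope) x observed baseline gap, where the slope is the pooled within-group regression of post on pre.

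**Step 6: can the planned baseline test detect the problem?** The standard error of a standardised baseline difference is √(1/7 + 1/6) = 0.556. The t test has 13% power for a 0.5 SD gap and 37.5% for 1 SD. Chance alone would give a gap above 0.5 SD 37% of the time.

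**The case against.** **The bias is conditional.** The gap, the correlation and regression to a common mean are all assumed, and with a stable gap the planned test is the unbiased one. This stands. It makes baseline adjustment a companion analysis, not a correction, and it means the actual bias in this trial is unknown. It does not rescue the plan, which gives the reader no way to see how far a result depends on baseline.

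**Under Bonferroni the excess is small.** At 0.05/9 a 1 SD gap gives 1.2 to 2.2% per outcome, and more comparisons would lower it further. This is true for the formal test, but the >75% rule lies outside that control.

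**The >75% rule is partly a separate problem.** It fires in 15/13/11% of trials with no gap, whatever the allocation. In relative terms, at ρ = 0.5 and a 1 SD gap, the Bonferroni test inflates more (about 3.9-fold against 2.9-fold). Both points are right. The absolute rise to 44/33/25% is still due to the gap.

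**The lack of randomisation is disclosed, and a hypothesis is not a conclusion.** Both are fair. The plan also assigns between-group differences to the ANOVA and not to the paired tests. But the disclosure is never carried into the design claim or the inference.

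**Side-by-side reporting has no threshold.** With no true gap, the two estimates are more than 0.2 SD apart in 42/25/16% of trials. That is so, but a chance gap in the observed groups also makes the result depend on baseline. The comparison should be read as that description and not as a test.

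**Conclusion.** The concern holds and should be fixed. The quoted passages establish a non-randomised 7 v 6 comparison, an experimental framing, an unadjusted change-score test, and a likelihood rule without multiplicity control. With no cuff effect, a regressing gap of 1 SD would produce an apparent benefit of 0.20 to 0.50 SD, and one of 0.5 SD would produce 0.10 to 0.25 SD, for pre-post correlations of 0.8 down to 0.5. These sizes rest on the assumed gap, correlation and regression to a common mean. The documents do not allow the actual direction or size to be determined. The conclusion that the planned contrast can be biased, and that the plan would not reveal it, does not depend on the particular values.

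**What to change.** 1. **Statistical analysis:** for each outcome, report the interaction (change-score) estimate and the baseline-adjusted ANCOVA estimate side by side with confidence intervals. Read disagreement as showing that the result depends on baseline differences. Do not require both to be significant.
2. **Baseline:** show the standardised baseline difference already planned beside each result. Do not take a non-significant baseline t test as evidence of balance. A statement of how the groups were formed, and of the losses from 37 to 13 by group, would help the reader judge this.
3. **Likelihood rule:** do not use the >75% rule or its labels as evidence of a cuff effect. If they are kept, present them as descriptive and for both estimates.
4. **Claims:** restate the design sentence in Methodology and the efficacy part of Hypothesis 6 as *an exploratory, non-randomised comparison of walking with and without the cuff*, with non-causal conclusions. Base any statement about the cuff on the between-group contrast, not on the paired tests.

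**Cost.** No new data: one extra model per outcome, one residual degree of freedom (11 to 10) and a weaker claim. For ρ = 0.5/0.7/0.8, the mean 95% half-width of ANCOVA is 1.10/0.91/0.76 SD with no gap and 1.25/1.03/0.87 with a 1 SD gap. The interaction gives 1.20/0.93/0.76 in both cases. Item 3 gives up a sensitive screen: for a true 1 SD effect with no gap, the >75% rule fires in 77/88/94% of trials, while the interaction has 37.5/56.2/73.5% power at 0.05 and 10/20/34% at 0.05/9. Neither estimate protects against groups that would have diverged anyway.

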1- The training program has a positive impact on quality of life and functional autonomy in people with fibromyalgia.

2- The training program is effective and generates little fatigue.

3- The training program has a high adherence in people with fibromyalgia.

4- The hypoxia produced and the relative intensity of the program has a direct impact on the balance of oxidant/antioxidant levels.

5- The levels of TAS, MDA, liver enzymes, biochemical variables and hemogram remain stable without significant alterations.

6- Occlusive training in people with fibromyalgia proves to be an effective and safe therapy as part of the treatment.

Objectives

Main Objective

To improve the quality of life and functional autonomy.

Specific Objectives

- 1- To achieve results by minimizing the fatigue produced in people with fibromyalgia.

- 2- To get people accustomed to the adapted program and make it part of their routine.

- 3- To measure variables in blood/plasma to verify the results obtained for a better understanding of the disease and its impact.

- 4- To identify those blood/plasma variables most susceptible to occlusive training that will allow a better understanding of fibromyalgia disease.

- 5- To test the effectiveness and adherence of occlusive training in people with fibromyalgia by means of blood/plasma samples, functional tests and questionnaires.

- 6- To evaluate occlusive training as a valid physical complementary therapy for people with fibromyalgia.

Methodology

The methodology will be carried out by an experimental design research to test the effect of the independent variable on the dependent variable. In this case, the independent variable will be the pressure exerted by the occlusive cuff on the thigh musculature during the planning of aerobic exercise walking of low intensity and reduced time, and its impact on the dependent variable, which is determined by plasma and blood values, mitochondrial protein expression, standardized questionnaires of the impact of the disease (psychometric), and functional tests of physical condition (distances and times performed), which will be measured before and after the intervention period.

Study population

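### The cuff is assigned by a non-randomized division with no stated rule, timing or concealment and no baseline adjustment, yet the plan reads the comparison as an experimental test of the cuff's effect.

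*Combined protocol and SAP*

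**What the plan says.** **Allocation.** The Participants' arms section reads: "Participants were divided into 2 non-randomized groups", with 37 people at baseline and 13 remaining after exclusions. One group is to "perform the occlusive cuff intervention period. n= 7 participants"; the other "will perform the intervention period without the occlusive cuff. n= 6 participants". The combined protocol and SAP gives no assignment rule, sequence, list-holder or time of assignment, and describes no matching, concealment or blinding.

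**Claim.** The Methodology section states: "The methodology will be carried out by an experimental design research to test the effect of the independent variable on the dependent variable". It names cuff pressure as the independent variable. Hypothesis 6 expects occlusive training to prove effective and safe. Both groups walk and differ only in the cuff, so any effect credited to the cuff rests on the between-arm contrast.

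**Analysis.** The Statistical analysis section has two relevant steps. For baseline: "To compare baseline variables the Student's t test, standardized differences" with 90% limits. For the arms: "multiple 2 x 2 (group x time) mixed-analysis of variance was performed", with a Bonferroni division. No baseline covariate or other confounder adjustment is mentioned.

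**The concern.** A comparison of arms estimates the effect of the cuff only if the arms would have changed alike without it. Random allocation supports that on average. A division by an unstated rule does not, whoever made it: staff judgement, participants' preference or session scheduling could each put people with different prospects into different arms.

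The group-by-time analysis removes a constant baseline difference. It does not remove regression to the mean, or a difference in expected change linked to traits such as motivation or tolerance of the cuff. Tolerance is not a listed baseline variable. Motivation is recorded only session by session during the intervention, as additional information.

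At stake is Hypothesis 6. A difference between arms could reflect who was in each arm, and a real effect could be masked for the same reason. As written, a reader cannot judge the direction or size of that error.

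**Working it through.** **The plan's own figure.** The only stated calculation is the sample size: 1.96² × 0.018 × 0.982 / 0.03² = 75.4, which agrees with the stated 75. It is a precision formula for a prevalence and says nothing about allocation or the 7 v 6 comparison.

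**Step 1: can the baseline check reveal an imbalance?** Inputs: arms of 7 and 6 (Participants' arms); two-sided 0.05 (sidedness is not stated, so this is assumed); 11 degrees of freedom, critical t 2.201. The noncentrality is d × √(7 × 6 / 13) = 1.797d.

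| True baseline imbalance d | Power of the baseline t test |
|---|---|
| 0.5 SD | 13% |
| 1.0 SD | 38% |
| 1.71 SD | 80% |

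The planned standardized differences do not depend on significance, but they are imprecise. The standard error is √(1/7 + 1/6) = 0.556 SD, so the 90% limits are about ±1.796 × 0.556 = ±1.0 SD.

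**Step 2: what can a baseline imbalance do to the change score?** Let r be the pre-post correlation, which is not in the documents. If the arms are drawn from one population and sorted on the baseline value, an imbalance b creates a spurious difference in change of (1 − r) × b, through regression to the mean.

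| r (assumed) | Spurious change from b = 0.5 SD | b that alone reaches 0.2 SD |
|---|---|---|
| 0.4 | 0.30 SD | 0.33 SD |
| 0.6 | 0.20 SD | 0.50 SD |
| 0.8 | 0.10 SD | 1.00 SD |

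The 0.2 SD is the smallest practically worthwhile difference in the Statistical analysis section.

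**Step 3: worst-case illustration of selection on a trait.** Suppose all 13 people are ranked on a trait and the top 7 go to one arm. By simulation, the arms then differ by about 1.5 SD on the trait (1.505). With correlation ρ between trait and change, the bias is 1.505 × ρ. If the sorting score correlates only k with the trait, it is 1.505 × k × ρ.

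- ρ = 0.3, k = 1: 1.505 × 0.3 = 0.45 SD.
- ρ = 0.3, k = 0.5: 1.505 × 0.5 × 0.3 = 0.23 SD.
- ρ = −0.3: the same sizes with the opposite sign.

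These are in SDs of the change score, which equals the between-subject SD when r = 0.5. For other r, multiply by √(2(1 − r)): at r = 0.8 the factor is 0.63, giving 0.29 and 0.14 SD. The partial-sorting figure therefore stays above 0.2 SD for r up to about 0.6.

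**Step 4: effect on the plan's decision rules when the cuff does nothing** (simulation, r = 0.5, pooled t with 11 degrees of freedom, substantial benefit meaning more than 75% probability of exceeding 0.2 SD).

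| Assignment | Substantial benefit declared | Two-sided p < 0.05 |
|---|---|---|
| Random | 15% | 5% |
| ρ = 0.3, partial sorting (k = 0.5) | about 27% | 6.6% |
| ρ = 0.3, perfect sorting | about 41% | 12% |
| ρ = −0.3, perfect sorting | 3% | 12% |

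The p-value column is before the Bonferroni division. If nine comparisons are assumed (four questionnaires, five fitness tests), the rates are 0.6% under random assignment and 1.9% under perfect sorting at ρ = 0.3.

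**The case against.** **The design is disclosed.** The plan says outright that the groups are not randomized, and experimental can mean only that a variable is manipulated. This stands as a defence against any charge of hiding the design. It does not answer the point, because the plan still tests for an effect and expects the training to prove effective, with no assignment rule and no adjustment.

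**Staff steering is not shown.** A reader might infer that staff placed people according to how well they tolerated the cuff, since everyone handles it before training: "Familiarization with the material will be completed when each volunteer is able to put on", set the pressure and walk. The documents do not support that. They do not say who divided the participants, or whether this came before or after familiarization. Completing familiarization also requires basic tolerance, which narrows the range left to sort on. Nor does the fall from 37 to 13 show steering: discretionary exclusions shape who is in the study, and affect the contrast only if the intended arm was already known.

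**The figures are an upper bound.** Perfect sorting is extreme and no document fixes ρ. A reader might also infer that the bias favours the cuff. Fitter participants may have less room to improve, in which case it runs the other way. The 15% rate under random assignment comes from the 75% rule, not from allocation, and the Bonferroni division keeps the p-value rates low. All of this stands, so the figures are illustrations only.

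**Randomizing 13 people leaves chance imbalance.** True: the chance of more than 0.5 SD on a given covariate is about 37%. The planned tests allow for chance imbalance; they do not allow for systematic selection.

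**Conclusion.** The point holds in this form: the arms are formed without randomization, by an unstated rule at an unstated time, and compared without baseline adjustment, while the plan reads the contrast as a test of the cuff's effect. Selection of unknown size and direction can enter that contrast, and the baseline check is too weak at 7 v 6 to give reassurance.

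The power figures rest only on the stated arm sizes and a two-sided 0.05 level. The bias figures rest on assumed correlations and on how strongly assignment tracked the trait; they show what is possible, not what happened. No conclusion that anyone steered participants, or that the result will favour the cuff, is supported. A larger sample or a different significance test would not remove the problem.

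**What to change.** **If allocation is still open.** In Participants' arms, replace the division with a computer-generated random list, held by an existing team member who neither recruits nor tests, and released for each person after eligibility is confirmed and the Week 1 baseline is complete. Cost: one paragraph and a list. Both arms already follow the same stages, so logistics hardly change; participants lose any choice of arm.

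**If allocation is already made**, as the past tense and the final arm sizes suggest:

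- In Methodology, call the design non-randomized (quasi-experimental).
- In Participants' arms, state how, when and by whom people were assigned, including whether this came before or after the exclusions and the cuff familiarization.
- In Statistical analysis, compare the arms on each outcome adjusted for its own baseline value (ANCOVA). The baseline questionnaires, blood measures and functional tests are already collected. The cost is one residual degree of freedom (13 − 2 = 11 becomes 13 − 3 = 10). This addresses measured baseline differences, not selection on unmeasured traits.
- Limit Hypothesis 6 to an association.

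This route costs wording, one model term and a weaker claim.
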